**ABBREVIATIONS AND DEFINITIONS OF TERMS**

AE	Adverse event
AT	Adenotonsillectomy
DS	Down syndrome
OSAS	Obstructive sleep apnea syndrome
PAP	Positive airway pressure

---

## ABSTRACT

Context: (Background)

- OSAS is very common in children with DS
- OSAS in children with DS does not resolve after adenotonsillectomy
- Many children with DS and OSAS require treatment with PAP

Objectives: (primary and important secondary objectives)

- Identify the perceptions, beliefs, and family-relevant outcomes regarding the treatment of OSAS with PAP in children with DS

Study Design:

- Cross-sectional study

Setting/Participants:

- The study will be performed at CHOP and Cincinnati Children's Hospital Medical Center (CCHMC) outpatient setting
- Caregivers of children with DS and OSAS aged 6-17.5 years treated with PAP

Study Interventions and Measures:

- Open-ended semi-structured interviews

**TABLE 1: SCHEDULE OF STUDY PROCEDURES**

Study Phase	Screening & Interview
Informed Consent	X
Review Inclusion/Exclusion Criteria	X
Semi-structured open-ended interview	X

## 1 BACKGROUND INFORMATION AND RATIONALE

### 1.1 Introduction

Down syndrome (DS) is a common disorder, occurring in 1 per 800 births, which translates to approximately 5,400 children with DS born in the USA annually. Hallmarks of the syndrome include intellectual disability, hypotonia and craniofacial anomalies, and congenital cardiac defects occur in 50% of individuals. Common comorbidities include hypothyroidism, obesity, and the obstructive sleep apnea syndrome (OSAS). Untreated OSAS is associated with significant morbidity such as growth failure, systemic, and pulmonary hypertension, endothelial dysfunction, and cognitive and behavioral deficits. Median life expectancy in individuals with DS has increased from 25 years in 1983 to 58 years in the present day. While this represents a significant advance in health, individuals with DS still have early mortality compared to the general population. It is therefore incumbent upon health care practitioners to diagnose and treat comorbidities, such as OSAS, in order to optimize health and cognitive/behavioral function, increase survival, and maximize health-related quality of life. Individuals with DS are predisposed to OSAS due to craniofacial features (midface hypoplasia, glossoptosis), hypotonia, comorbid obesity, and hypothyroidism. Studies have shown a prevalence of OSAS in children with DS between 45 and 55%. These rates are markedly higher than that of typically developing children in whom the prevalence of OSAS is about 2%.

Adenotonsillectomy (AT) is considered first-line treatment for childhood OSAS. However, available data indicate that polysomnography (PSG) improves in only a portion of children with DS after AT. In fact, many children with DS are referred for positive airway pressure (PAP) therapy initiation due to persistent OSAS after AT, and PAP appears to be an important feature of the experience of living with DS. PAP has been shown to be highly effective at resolving polysomnographic manifestations of OSAS in children and adolescents, including those with DS and other disabilities. However, PAP as a treatment for OSAS has not been well-studied in children with DS. Furthermore, patient/family reported outcomes are an important knowledge gap long overdue in this population.

### 1.2 Relevant Literature and Data

**DS Prevalence and morbidity:** Down syndrome (DS) is a common disorder, occurring in 1 per 800 births, which translates to approximately 5,400 children with DS born in the USA annually. Hallmarks of the syndrome include intellectual disability, hypotonia and craniofacial anomalies. Congenital cardiac defects occur in 50% of individuals. Common comorbidities include hypothyroidism, obesity, and obstructive sleep apnea syndrome (OSAS). DS is also associated with premature death and early-onset Alzheimer's disease. Median life expectancy has increased from 25 years in 1983 to 58 years in the present day. While this represents a significant advance in health, individuals with DS still have early mortality compared to the general population.

**DS and OSAS:** Individuals with DS are predisposed to OSAS due to craniofacial features (midface hypoplasia, glossoptosis, hypotonia), comorbid obesity, and hypothyroidism. Studies have shown a prevalence of OSAS in children with DS between 45 and 55%.

These rates are markedly higher than that of typically developing children in whom the prevalence of OSAS is about 2%. Untreated OSAS is associated with significant morbidity such as growth failure, systemic and pulmonary hypertension, endothelial dysfunction, and cognitive and behavioral deficits. It is therefore incumbent upon health care practitioners to diagnose and treat comorbidities, such as OSAS, in order to optimize health and cognitive function, increase survival, and maximize health-related quality of life in youth with DS and OSAS.

**Treatment of OSAS in Children with DS:** Given the high prevalence of OSAS, the American Academy of Pediatrics published a clinical report focused on the care of children with DS in 2011. In this guideline, they advised families to assess for OSAS as soon as 6 months of age and emphasized the poor correlation between parental history and sleep study results. Therefore, they recommended that all children with DS undergo a sleep study by 4 years of age, and that pediatricians discuss the impact of obesity as a risk factor for OSAS. Adenotonsillectomy (AT) is considered first-line treatment for childhood OSAS. However, available data indicate that polysomnography (PSG) improves in only a portion of children with DS after AT. In fact, many children with DS are referred for positive airway pressure (PAP) therapy initiation due to persistent OSAS after AT. PAP has been shown to be highly effective at resolving polysomnographic manifestations of OSAS in children and adolescents, including those with DS and other disabilities. Importantly, studies indicate that PAP also reduces symptoms of OSAS and improves school performance, behavior, mood, daytime sleepiness and quality of life (QOL) in typically developing children and adolescents. Another important consideration is that PSG results may not predict patient-reported outcomes and other physiological responses, indicating a need for studies that inform the medical community not only about healthcare provider-relevant outcomes but also about family-relevant outcomes related to the experience of living with DS and OSAS. In addition, RCTs that examine a range of relevant qualitative, clinical and physiological outcomes are lacking. These studies, such as the current proposal, could inform families and the medical community about variation in responses and provide the framework for developing a “precision medicine” approach for future single- or multiple-staged approaches, matching the best intervention to the individual child defined by appropriate family-relevant, clinical, physiological and/or genetic factors.

**PAP adherence in children with DS:** There is a dearth of literature regarding PAP adherence in children, and even less in children with DS. Generally, PAP is inherently difficult for individuals to use regularly. In addition to the daily burden of putting the equipment on each night and discomfort of wearing a mask with pressurized air being administered while sleeping, common side-effects include nasal symptoms (e.g., nasal dryness, rhinorrhea, congestion and epistaxis), eye irritation, skin pressure sores or dermatitis, and aerophagia. Some patients suffer from feeling closed-in by the mask (e.g., claustrophobia). Not surprisingly, PAP efficacy is limited by poor adherence. Most studies in the pediatric age range have encompassed a wide age spectrum and heterogeneous populations, and have reported improved adherence over time. Importantly, the few studies, all retrospective, including children with DS under the larger umbrella of children with developmental disabilities (DD), have shown better adherence in children with DD compared to typically developing children. Hawkins et al reported that DD was a positive predictor factor for PAP adherence (OR = 2.55, 95%CI = 1.27–5.13; p = 0.007), and our group has showed that at 3 months after PAP initiation, adherence was 86.7% [33.9-

97.9%] of nights in children with developmental disabilities and 62.9% [30.8-87.8%] in typically developing children ( $p=0.01$ ).

### **1.3 Compliance Statement**

This study will be conducted in full accordance all applicable Children's Hospital of Philadelphia Research Policies and Procedures and all applicable Federal and state laws and regulations including 45 CFR 46. All episodes of noncompliance will be documented.

The investigators at CHOP and CCHMC will perform the study in accordance with this protocol. CHOP investigators will obtain verbal consent, CCHMC will obtain written consent, and will report unanticipated problems involving risks to subjects or others in accordance with Children's Hospital of Philadelphia IRB Policies and Procedures and all federal requirements. Collection, recording, and reporting of data will be accurate and will ensure the privacy, health, and welfare of research subjects during and after the study.

## **2 STUDY OBJECTIVES**

The purpose of this multi-center study is to further characterize the experience of living with DS and OSAS.

### **2.1 Primary Objective (or Aim)**

- The primary objective of this study is to identify the perceptions, beliefs, and family-relevant outcomes regarding the treatment of OSAS with PAP in children with DS.

## **3 INVESTIGATIONAL PLAN**

### **3.1 General Schema of Study Design**

Cross-sectional study

### **3.2 Study Duration, Enrollment and Number of Sites**

This is a multi-center outpatient study to be performed at 2 clinical sites: Children's Hospital of Philadelphia and Cincinnati Children's Hospital. Forty Caregivers of children with DS and OSAS treated with PAP and their children will be enrolled. The study comprises one 30-minute open-ended semi-structured interview per caregiver. The duration of the interview is approximate. It will last up to 30 minutes as some families may want to include more details.

### **3.3 Total Number of Study Sites/Total Number of Subjects Projected**

#### **3.3.1 Duration of Study Participation**

The study duration per subject will be 1 day.

#### **3.3.2 Total Number of Study Sites/Total Number of Subjects Projected**

The study will be conducted at two investigative sites in the United States.

Recruitment will stop when approximately 40 subjects are interviewed. It is expected that approximately 40 subjects will be enrolled to produce 30 evaluable subjects.

### **3.4 Study Population**

Adult caregivers of children with DS and OSAS and their children will be the participants of this study. The inclusion/exclusion criteria below include required characteristics of the children to consider their caregiver eligible for participation.

#### **3.4.1 Inclusion Criteria-Patients**

- 1) Children with DS and OSAS treated with PAP for at least 6 months
- 2) Children aged between 6 and 17.5 years
- 3) English proficiency

#### **3.4.2 Exclusion Criteria-Patients**

- 4) In foster care
- 5) Diagnosed with major illness, such as leukemia or severe cyanotic congenital heart disease listed for cardiac transplant as these severe diseases may add confounders

#### **3.4.3 Inclusion Criteria-Caregivers**

- 6) Parent or legal guardian of an eligible patient subject
- 7) English proficiency
- 8) Must live with the patient subject at least 4 nights of the week

#### **3.4.4 Exclusion Criteria- Caregivers**

- 9) Foster parent

Subjects that do not meet all of the enrollment criteria may not be enrolled. Any violations of these criteria must be reported in accordance with IRB Policies and Procedures.

## **4 STUDY PROCEDURES**

### **4.1 Screening and Interview**

- Informed Consent
- Medical record review
- One semi-structured 30 minute open-ended interview per participant will be conducted over the phone. The interview will be audio-recorded

#### **4.1.1 Visit 1**

- Open-ended semi-structured interviews will be conducted over the phone and audio recorded.

### **4.2 Unscheduled Visits**

Due to the nature of this study, unscheduled visits are not expected

### **4.3 Subject Completion/Withdrawal**

Subjects may withdraw from the study at any time without prejudice to their care. They may also be discontinued from the study at the discretion of the Investigator if they fail to keep the phone interview appointment repeatedly. The Investigator or the Sponsor (if applicable) may also withdraw subjects who violate the study plan, or to protect the subject for reasons of safety or for administrative reasons. It will be documented whether or not each subject completes the clinical study. If the Investigator becomes aware of any serious, related adverse events after the subject completes or withdraws from the study, they will be recorded in the source documents and on the CRF.

#### **4.3.1 Early Termination Study Visit**

Subjects who withdraw from the study will not have the interview as this is the only study procedure.

## **5 STUDY EVALUATIONS AND MEASUREMENTS**

### **5.1 Screening and Monitoring Evaluations and Measurements**

#### **5.1.1 Medical Record Review**

- Date of birth of child
- Race, ethnicity, maternal education of child and parent
- Zip code of the family
- Sleep study results of child
- PAP information of child: date of initiation of treatment, titration study, adherence

- Child comorbidities

## 5.2 Interview

Semi-structured interviews will explore such key constructs as knowledge/belief about OSAS and PAP therapy, routines and resources that promote or limit PAP use, barriers, self-efficacy, and communication and attitudes about PAP. The interviews will be performed with the parent and that they will be audio-recorded.

## 5.3 Safety Evaluation

Data safety will be strictly monitored during the study. Because of the nature of the study, no other safety issues are anticipated.

# 6 STATISTICAL CONSIDERATIONS

## 6.1 Primary Endpoint

The primary endpoint will be completing the interviews.

## 6.2 Control of Bias and Confounding

For this mixed methods research, all caregivers meeting criteria will be contacted. The first forty confirming participation and providing consent will be included in the study.

## 6.3 Statistical Methods

### 6.3.1 Baseline Data

Baseline and demographic characteristics will be summarized by standard descriptive summaries (e.g. means and standard deviations for continuous variables such as age and percentages for categorical variables such as gender).

### 6.3.2 Analysis of Interviews

Data Analysis: Interviews will be transcribed by Datagain, a professional transcription company. Audio files are loaded onto a secure site. In the process of transcription, all identifying information will be removed. Password protected transcripts are returned to the Mixed Methods Research Lab where they are loaded into a password protected NVivo file on a secure server in the Department of Family Medicine and Community Health. Datagain has a business use agreement with the University of Pennsylvania. Once transcripts are verified for accuracy, the audio file will be destroyed. The study team will create a codebook by conducting a line by line reading of the first five transcripts. The investigators will identify key ideas in the transcripts and will use these key ideas to form codes. Each code will be operationalized and decision rules for their application will be included in the definition. Once the codebook is stabilized, the team will double code the first five transcripts and will use the interrater reliability function in NVivo to ascertain agreement.

Once 95% agreement has been achieved, the team will code the remaining transcripts, checking interrater reliability every fifth transcript.

Coded data will be summarized, examined for patterns and used to identify factors associated with adherence and non-adherence as well as implementation.

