## **6.4 Sample Size and Power**

In qualitative research, sample size is dictated by the principle of saturation. Saturation is when no new themes arise among each of the key subgroups in the sample. Several factors dictate an estimation of when saturation might be achieved. Key among these is the degree of homogeneity within the sample. Since the families we will recruit are all dealing with a similar set of issues and similar clinical contexts, we anticipate that saturation will be likely with up to 15 families per site. We will conduct our analysis concurrent with data collection, using the constant comparative method. In this approach, we iteratively move between codes and texts, constantly looking for examples of existing ideas and being alert to new ones. This process enables us to learn when no new ideas emerge within the group as a whole and within each site. Although in our experience we typically achieve saturation with approximately 15 interviews per group, we have allowed for up to 20 interviews per site so that we can assure that saturation has been achieved.

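### The 95% agreement gate, read as percent agreement, cannot by itself show reliable coding for uncommon codes

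*Combined protocol and SAP*

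**What the plan says.** All of this is in section 6.3.2 (Analysis of Interviews) unless noted.

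- **Codebook.** "The study team will create a codebook by conducting a line by line reading of the first five transcripts". "Each code will be operationalized and decision rules for their application will be included in the definition".
- **Reliability check.** Once the codebook is stable, "the team will double code the first five transcripts and will use the interrater reliability function in NVivo to ascertain agreement".
- **Gate and rechecks.** "Once 95% agreement has been achieved, the team will code the remaining transcripts, checking interrater reliability every fifth transcript".
- **Use of the codes.** "Coded data will be summarized, examined for patterns and used to identify factors associated with adherence and non-adherence as well as implementation".
- **Volume.** Section 6.4 states: "we have allowed for up to 20 interviews per site so that we can assure that saturation has been achieved". With two sites that is at most 2 × 20 = 40 transcripts, so up to 40 − 5 = 35 are coded after the gate.

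No section names kappa, positive agreement or any other chance-corrected measure. Nor does any section say what unit of text is compared, whether agreement is taken per code or pooled over codes, or what follows if a later check is poor.

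**The concern.** In this study the codes are the measurements, and agreement between coders is the only quantitative evidence that a code means the same thing to both. Percent agreement counts text that neither coder marked as agreement. For a code that applies to a small part of an interview, nearly all the text is of that kind, so the percentage is high whether or not the coders mark the same places.

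Specific barriers, or particular reasons for not using PAP, could be codes of this type. A gate that passes them almost automatically says little about whether they were identified consistently, yet they would feed the search for patterns linked to adherence. They also bear on the saturation judgement in section 6.4, which depends on recognising when ideas stop being new. If agreement is pooled over codes, which is not stated, poor agreement on one code could be hidden further.

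**Working it through.** The 95% is a chosen threshold with no derivation, so there is no planned figure to reproduce. The check asks what 95% implies for a single code.

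**Inputs.** The threshold of 95% is from section 6.3.2. The share of text to which a code applies is not in the documents; it is an assumption, varied from 1% to 50%. The text unit is also assumed: shares below are shares of whatever units are compared.

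**Formulas.** Let the coders apply a code to shares p1 and p2 of the text, and both to share b.

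- Observed agreement: Po = 1 − (p1 − b) − (p2 − b)
- Chance agreement: Pe = p1·p2 + (1 − p1)(1 − p2)
- Cohen's kappa = (Po − Pe)/(1 − Pe)
- Positive agreement = 2b/(p1 + p2)

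**Step 1: no overlap (b = 0), equal use p.** Then Po = 1 − 2p.

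- p = 1%: Po = 98.0%, kappa = −0.01. Passes.
- p = 2.5%: Po = 95.0%, Pe = 0.025² + 0.975² = 0.95125, kappa = (0.95 − 0.95125)/0.04875 = −0.03. Passes.
- p = 3%: Po = 94.0%. Fails.

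In counts, take 1,000 units of text, of which each coder marks a different 25. They disagree on 50 and agree on 950, which is 95%, without one shared mark.

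**Step 2: one coder never uses the code.** With p1 = 5% and p2 = 0, Po = 95.0%, Pe = 0.95 and kappa = 0. Passes.

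**Step 3: independent random marking.** Expected agreement is 1 − 2p(1 − p). It is 95% or more when 2p(1 − p) ≤ 0.05, that is p ≤ about 2.57%.

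**Step 4: agreement of exactly 95%, equal use.** Here b = p − 0.025.

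| Share p | Pe | Kappa | Positive agreement |
|---|---|---|---|
| 2.5% | 0.951 | −0.03 | 0 |
| 3% | 0.942 | 0.14 | 0.17 |
| 5% | 0.905 | 0.47 | 0.50 |
| 10% | 0.820 | 0.72 | 0.75 |
| 15% | 0.745 | 0.80 | 0.83 |
| 20% | 0.680 | 0.84 | 0.88 |
| 30% | 0.580 | 0.88 | 0.92 |
| 50% | 0.500 | 0.90 | 0.95 |

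At p = 5%, both coders mark 2.5% of the text and at least one marks 7.5%, so only a third of the text marked by either is marked by both.

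**Step 5: where 95% corresponds to a given kappa.** Setting Po = 0.95 and kappa = k gives 1 − Pe = 0.05/(1 − k), and with equal use 1 − Pe = 2p(1 − p).

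- k = 0.60: 2p(1 − p) = 0.125, so p ≈ 6.7%.
- k = 0.80: 2p(1 − p) = 0.25, so p ≈ 14.6%.

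**The case against.** **The metric is inferred.** The plan does not use the words raw or percent agreement; it says the team "will use the interrater reliability function in NVivo to ascertain agreement" and gives a percentage. If a kappa of 0.95 was meant, the point falls. This stands as a limit on certainty, but percent agreement is the plain reading and nothing in the documents suggests otherwise.

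**Prevalence and unit are unknown.** The share a code occupies depends on the unit: a code that is rare by characters may be common by response or by transcript. On a coarse unit, few or no codes might fall in the zone where the gate is empty. This also stands, and it is why the result is conditional.

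**Zero overlap is a limiting case.** Codes have written decision rules, the codebook is stabilised before double coding, reliability is rechecked, and section 6.4 adds constant comparison. These lower the practical risk. They do not make the gate itself more discriminating, and the rechecks have no action level of their own.

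**The consequences are limited.** The primary endpoint in section 6.1 is completion of the interviews, the coded data are examined descriptively, and section 5.1.1 takes PAP adherence from the medical record. That is correct. However, the objective in section 2.1 concerns perceptions, beliefs and outcomes that matter to families, and those reach the results through the codes.

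**Kappa has faults too.** For a rare code in five transcripts it rests on few marked segments and is imprecise. That is a reason to pair it with positive agreement, not to rely on percent agreement.

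A reader might go further and infer that the adherence patterns will rest on unreliable coding, or that the gate is uninformative for every theme. The documents support neither. They give no code frequencies, and for codes covering about 15% of the text or more, used similarly by both coders, 95% agreement already means kappa of about 0.80 or higher.

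**Conclusion.** The concern holds for uncommon codes. Taken as percent agreement, the 95% criterion can be met with no shared coding when the two coders' shares sum to 5% of the text or less. At exactly 95%, the same pass mark spans kappa from about zero to 0.90, depending on a prevalence that the plan does not give.

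The conclusion rests on three assumptions: that 95% means percent agreement, that the coders use a code about equally often (for the tabulated kappas), and that some codes cover only a few percent of the units compared. Under these, passing the gate is not evidence of reliability for those codes. It is not evidence of unreliability either. The weakness is worth correcting before double coding, because the remedy uses data the team already plans to collect.

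**What to change.** Amend section 6.3.2 as follows.

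1. State the text unit on which coders are compared.
2. Judge reliability code by code, using Cohen's kappa and positive agreement. Keep percent agreement as a descriptive figure beside them.
3. Set the threshold before double coding, for example kappa of at least 0.60 for each code. The value is the team's choice; the documents do not imply one.
4. Where a code falls short, or is too rare to estimate, refine its definition and settle the disagreements by consensus. Do not merge or drop it automatically, since that could remove the uncommon barriers the study hopes to find.
5. Apply the same statistics and the same action at each fifth-transcript check.
6. Report the values for each code.

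The cost is a change of wording, computed from double coding already planned, with no new participants or data. The downsides are a possible extra round of refining definitions, imprecise kappa for rare codes, and a reported figure that looks less favourable than 95%. If the team did intend a chance-corrected 0.95, the statistic should be named, and items 1, 4, 5 and 6 would still be useful.
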